5.1 Attrition and Nonresponse

Despite our efforts, some attrition and missing data are likely. The linear mixed model does allow missing data and provides valid results under the assumption of missing at random (MAR). MAR means that the missingness can be related to model covariates as well as observed values of the dependent variable, and is sometimes termed "ignorable" missingness. As Molenberghs et. al. (2007) detail, MAR is a relatively weak and non-restrictive assumption about the missing data. Nonetheless, the possibility of non-ignorable missingness cannot be ruled out and so, as advocated by Molenberghs et. al. (2007), we will conduct sensitivity analyses using non-ignorable pattern-mixture and selection models to investigate the robustness of our conclusions across these different models for missing data. This approach will follow our detailed exposition in Chapter 14 of our text (Ackermann & Marrero, 2007).

5.2 Sample Size and Power

We base power on our primary endpoint: weight change from baseline to the 6-month timepoint. Our interest is in identifying the intervention components that make a more than minimal contribution to average weight loss, or conversely to identify those components that have minimal or no effect on weight loss. Our operational definition of more than minimal is a component effect size of .25 (mean difference divided by standard deviation). Thus, we have powered the study to detect effects of .25 or greater. Using the standard deviation estimate of 4 kg from Amundson et al (2009), which had a follow-up time similar to ours, this translates to a 1 kg difference in weight loss; we view weight loss of less than 1 kg as a minimal effect. There are five components in our 2^{5-1} fractional factorial design. Based on the minimal detectable effect size of .25, the total sample size will be 560 subjects. Based on our previous MBC and PDA+ studies, we conservatively assume an attrition rate of 10% at the 6-month timepoint, so that there will be approximately 504 subjects at this timepoint. Thus, each of the component main effect estimates will be based on 504 subjects, that is, 252 subjects in each of the two levels of the component. Based on these assumptions, we can detect a main effect or interaction effect size of .25 for each component with 80% power under a two-tailed hypothesis test.

Based on our current enrollment as of January 2017, approximately 45% of consented participants were eligible to be randomized after screening. We estimate that we will need to consent approximately 1250 subjects in order to obtain 560 eligible participants for randomization. Of the 560 eligible participants randomized, all will be asked to find a "Buddy" to participate in the study. We are estimating that approximately 850 "Buddies" will need to be verbally consented. (1250 participants + 850 Buddies = 2100 total to be consented).

5.3 Interim Monitoring Plan

The DSMB will have overall responsibility for monitoring the emerging results. The focus of the DSMB will be on safety issues, recruitment, retention, protocol adherence and data quality and timeliness. The DSMB will meet twice each year, and more frequently if needed. Any explicit stopping rules for harm will be determined by the DSMB. In addition, futility as defined by low conditional power to show a benefit given the outcome data to date will not be assessed. However, recruitment will be monitored by the DSMB and the recommendations of the group will be sought if accrual is falling below the goal needed to complete the project by the conclusion of funding.

For each meeting, a formal detailed statistical report will address all aspects of the trial, including baseline variables, outcome variables, compliance with the protocol, data quality, loss to follow-up (primary outcome missing), and protocol violations (such as randomization of ineligible patients). Outcomes will be reported in a cohort of patients randomized before a given date. All adverse events reported to date will be included, with an indicator showing new events since the previous meeting. Adverse events may be reported to some or all of the DSMB members on a more frequent basis if applicable, as requested by the DSMB.

The DSMB will also consider new information from external sources such as the results of other randomized trials and results of meta-analyses of similar interventions. If this new information is judged relevant to all patients, the DSMB may recommend changes to the protocol or to the consent form.

5.4 Handling Early Termination/Censoring

Patients can choose to withdraw from the study at any time. However, all participants randomized to the intervention will be accounted for in all follow-up analyses following the intent-to-treat principle. If participants withdraw from the study, and do not agree to return for follow-up assessments, data from their most recent assessment will be carried forward and imputed in subsequent assessment points (Last Observation Carried Forward).

6 Data Collection

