All of the estimated main effects and interactions will be based on all 32 experimental conditions. For example, the main effect of Number of Coaching Sessions will be estimated by comparing the mean of Experimental Conditions with 12 coaching calls in Table 3 vs. the mean of Experimental Conditions with 24 coaching calls. Similarly, the main effect of PCP report will be estimated by comparing the mean of Experimental Conditions having PCP progress reports sent vs. the mean of Experimental Conditions not having PCP progress reports sent. Note that in each case, all experimental subjects are included in the estimate. That is why factorial experiments can have small sample size/condition and still have excellent power if the overall sample size is sufficiently large.

Primary Aim 1 is to test for differences in weight by intervention components across the timepoints (baseline, 3- & 6-months), under an intent-to-treat basis, using linear mixed models. For each of the five components, we will determine whether there is a difference in change across time using baseline as the reference cell (i.e., 3-months vs baseline and 6-months vs baseline). From one perspective this is a main effect of each component on the pre-post difference. However, statistically these effects will be modeled as component by time interactions, with the 6-month outcome as the primary endpoint. We will also include two way interactions between components (e.g., Component 1 by Component 2 by time interaction). We note that (a) testing 2-way interactions between intervention components is extremely novel, as traditional RCTs are not capable of looking at these effects, and (b) because we will be using effect (-1,1) coding rather

than dummy (0,1) coding, the power for tests of main effects and interactions are identical for effects of identical size. We expect that testing these effects will be valuable, as we may find, e.g., that two intervention components each have independent main effects, but that when combined they offer no incremental effect. Our plan for dealing with such cases is elaborated below.

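### Section 5.4 carries the last weight forward for participants who withdraw and decline follow-up, and this is not reconciled with the mixed-model handling of attrition in Section 5.1

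*Combined protocol and SAP*

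**What the plan says.** - **Section 5, Primary Aim 1 paragraph.** Weight at baseline, 3 and 6 months is analysed "under an intent-to-treat basis, using linear mixed models", with the 6-month outcome as primary endpoint. No imputation step is given.
- **Section 5.1.** On attrition and nonresponse: "The linear mixed model does allow missing data and provides valid results under the assumption of missing at random (MAR"). For departures from MAR, "we will conduct sensitivity analyses using non-ignorable pattern-mixture and selection models". Withdrawals are not excepted and LOCF is not mentioned.
- **Section 5.4.** The condition is "If participants withdraw from the study, and do not agree to return for follow-up assessments"; the consequence is "data from their most recent assessment will be carried forward and imputed in subsequent assessment points (Last Observation Carried Forward"). The preceding sentence applies the intent-to-treat principle to every follow-up analysis, so LOCF is not confined to a secondary or sensitivity analysis.
- **Section 5.2.** For planning, "we conservatively assume an attrition rate of 10% at the 6-month timepoint", "so that there will be approximately 504 subjects at this timepoint".
- **Scope.** Section 4.6.4 seeks permission to keep collecting outcomes after withdrawal, and Section 4.2.2 accepts a self-reported weight from those who cannot attend. Such participants have collected weights. Missed visits and lost contact without withdrawal fall only under 5.1.

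**The concern.** Two statisticians following this plan could build different primary datasets. One would leave the later weights of these participants missing, as 5.1 implies. The other would fill them in, as 5.4 says. Under the second, a participant who leaves before month 3 is entered with zero change and one who leaves later with the 3-month weight, both treated as measured at 6 months. With no 6-month value missing, neither the MAR handling nor the pattern-mixture and selection models can act on them, although people who refuse all further contact are a group for whom non-ignorable missingness is a real possibility.

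The choice matters because Step 1 of the Aim 2 decision process selects components by a significant main effect on weight. The rule should be fixed before the data are seen.

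**Working it through.** **1. The plan's own figure.** Inputs from 5.2: difference 1 kg, SD 4 kg, 560 randomised, 10% attrition. Two-sided alpha of 0.05 is assumed, since no alpha is stated.
- 560 × 0.90 = 504, or 252 per level.
- SE = 4 × √(2/252) = 0.356; 1/0.356 = 2.806; power = Φ(2.806 − 1.96) = 80.1%. The stated 80% is reproduced.
- With 280 per level and no dilution: SE = 0.338 and power = Φ(2.958 − 1.96) = 84.1%.

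The stated power therefore corresponds to 504 unimputed 6-month weights.

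**2. Assumptions for the comparison.** Only the 6-month SD of 4 kg, the 1 kg effect, the 10% attrition and the sample size come from the documents. Assumed: mean loss in the less effective level 3 kg at month 3 and 5 kg at month 6; 3-month SD 3 kg; correlation 0.8; 3-month effect 60% of the 6-month effect (so 3.6 and 6 kg in the more effective level); half of withdrawals before month 3; withdrawal random within level.

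**3. Closed form, if every dropout declines follow-up.** With withdrawal proportion w, the LOCF level mean is (1 − w) × M6 + 0.5 × w × M3.
- *Equal 10%, true effect 1 kg:* (0.9 × 6 + 0.05 × 3.6) − (0.9 × 5 + 0.05 × 3) = 5.58 − 4.65 = 0.93 kg.
- *12.5% in the more effective level, 7.5% in the other:* (0.875 × 6 + 0.0625 × 3.6) − (0.925 × 5 + 0.0375 × 3) = 5.475 − 4.7375 = 0.74 kg.
- *Reversed:* (0.925 × 6 + 0.0375 × 3.6) − (0.875 × 5 + 0.0625 × 3) = 5.685 − 4.5625 = 1.12 kg.
- *No true effect, 12.5% vs 7.5%:* 4.5625 − 4.7375 = −0.175 kg, against the level that loses more.

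**4. Power check for equal 10%.** The LOCF mixture variance is 0.9 × (M6² + 16) + 0.05 × (M3² + 9) − mean².
- Less effective level: 37.8 − 4.65² = 16.18. More effective level: 47.898 − 5.58² = 16.76.
- SE = √((16.18 + 16.76)/280) = 0.343; z = 0.93/0.343 = 2.71; power = Φ(2.71 − 1.96) = 77%.
- Weights left missing: the variance per level is 16 × (0.36/252 + 0.64/266) = 0.0614, where 0.64 = 0.8² and 266 have a 3-month weight. SE = √(2 × 0.0614) = 0.350; power = Φ(1/0.350 − 1.96) = 81-82%.

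**5. Simulation.** There were 4000 replicates per scenario, using maximum likelihood on the 3- and 6-month changes with a Wald test at 0.05. Dropouts who do not decline follow-up stayed missing. The documents do not give the share of dropouts who decline, so three values are shown.

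| Scenario | LOCF, share 100% / 50% / 25% | Weights left missing |
|---|---|---|
| Equal 10%, true 1 kg | 0.93 / 0.96 / 0.98 kg; power 77 / 79 / 80% | 1.00 kg; 82% |
| 12.5% vs 7.5%, more effective level loses more | 0.74 / 0.86 / 0.93 kg; power 58 / 69 / 75% | true value 1 kg |
| 12.5% vs 7.5%, more effective level loses fewer | 1.12 / 1.06 / 1.03 kg; power 90 / 86 / 84% | true value 1 kg |
| 12.5% vs 7.5%, no true effect | bias 0.17 / 0.09 / 0.05 kg; type I error 8 / 6 / 6% | about 5% |

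With equal attrition and no true effect there is no bias, and error is 5-6% under both rules.

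**6. Sensitivity at 100% share, changing one assumption at a time** (losses of 5 then 5 kg, or 3 then 6 kg; correlation 0.6; 25% or 75% of withdrawals before month 3). Equal attrition gives 0.91-0.95 kg and 75-79% power. Unequal attrition gives 0.68-0.79 or 1.07-1.17 kg by direction, and null error of 7-10%.

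**The case against.** **Section 5.4 does name a rule.** It identifies the group and says what happens to it. On an ordinary specific-over-general reading, 5.4 governs these participants and 5.1 governs the rest. That stands: a reader might infer that the plan has no rule for them, and the text does not support that. What remains is that the rule is a weak one for the primary model and that no passage ranks it against 5.1.

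**The 504 is not a third rule.** A reader might take "each of the component main effect estimates will be based on 504 subjects" as a competing missing-data rule, or as an arithmetic conflict with 5.4. It is a planning count, it reproduces, and it is consistent with unimputed data. A mixed model would also use dropouts' earlier weights, so 504 does not describe the analysis set either.

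**The harm may be small.** The group is limited by 3.5 (people unwilling to accept any condition are not randomised), by the pre-randomisation call in 4.1.1, by continued collection under 4.6.4 and 4.2.2, and by the retention measures in 4.5.1, which cites retention above 90%. Unequal refusal is not documented. It is plausible, since Section 3.2.1 itself regards more coaching sessions as a greater burden, but the documents give no rate by level.

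**MAR is also untestable.** If withdrawn participants stay at their last weight, LOCF is on target (0.93 kg in the equal-attrition case) and MAR is high (1.00 kg). This is a fair limit on the fix. The difference is that 5.1 already plans sensitivity analyses around MAR, and none is planned around LOCF.

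**Deleting LOCF would leave a gap.** Aim 1 also has the proportion reaching 7% weight loss. Section 5 gives no model for it, and the MAR argument is made for the linear mixed model. Section 5.4 is the only text that could supply a follow-up value for withdrawn participants there. This stands and shapes the fix.

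**Conclusion.** The point holds as an unreconciled and inferior rule for a limited group, and it should be fixed. Confidence is high that 5.4 and 5.1 are unreconciled. It is lower that material harm would follow, because that depends on quantities the documents do not give.

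At the planned attrition, equal across levels, LOCF mildly shrinks a true effect, costs at most about 4-5 points of power under the base assumptions, and creates no false effect. A reader might infer that 5.4 will produce spurious component effects, but the plan's own attrition figure does not support that. Bias of practical interest needs unequal refusal. It can then favour or penalise a component, so no systematic wrong selection is shown. It shrinks quickly as the share who decline follow-up falls.

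**What to change.** In Section 5.4, state that for the primary weight analysis participants who withdraw and decline follow-up stay in the mixed model with all their observed weights, that their later weights are left missing, and that Section 5.1 governs. Keep LOCF as a labelled sensitivity analysis rather than simply deleting it. In the same place, state which rule applies to these participants for the 7% weight-loss outcome in Aim 1.

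The cost is one or two sentences and one simple additional sensitivity run, with no new data or participants. The downside is that the primary estimate will be somewhat high if withdrawn participants truly stay at their last weight; the pattern-mixture and selection models in 5.1, or the retained LOCF analysis, would show this.

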6.1 Data Collection Forms

The majority of data collection will be electronic, but paper versions of all instruments will be available to be administered or used as a backup system in the event of technical difficulties with the electronic administration system. Electronic data collection forms will be developed in-house by the Data Manager and Study Coordinator and administered utilizing the RedCap data management system in conjunction with Northwestern University Biomedical Informatics Center (NUBIC) of the Northwestern University Clinical and Translational Sciences (NUCATS) program. These forms will capture all data elements described in this protocol at each study visit. Any paper documents collected will be stored in participants folders in a locked suite and cabinet within the Department of Preventive Medicine.

6.2 Data Entry, Management System, and Data Security

The majority of participant data (including all patient reported outcomes) will be collected using an online system (RedCap) housed at and maintained by Northwestern University Biomedical Informatics Center (NUBIC) of the Northwestern University Clinical and Translational Sciences (NUCATS) program. Redcap allows for a secure portal to complete all study-related forms including all self-report questionnaires. These data are stored behind an encrypted firewall, and automatically backed up. All database files will be password protected, and only study staff will have access to the study databases. Any paper data will be de-identified, and kept in the laboratory in a locked suite and cabinet. The legend for the codes will be stored in the laboratory in a locked cabinet on-site in access-controlled laboratory. All electronic data and records of those individuals who after screening are deemed ineligible for the study will be completely deidentified and retained in encrypted form on Northwestern University's secure server, within password protected folders to which only study personnel will have access. The study co-investigator, [name] at Pennsylvania State University, and her team are not involved in the human subjects research (intervention) portion of the study. Their involvement is limited to receipt of de-identified participant databases, which will be used for data analysis purposes. Penn State will not receive any linkages between participant study information and "readily identifiable" information (e.g., names). Additionally, our collaborators at UCLA will be receiving de-identified participant databases, which will be used to analyze data related to the research question: "What are the most robust predictors of weight loss within Opt-IN study participants?". UCLA will not receive any linkages between participant study information and "readily identifiable" information (e.g., names, addresses).

6.2.1 Quality Control

All study assessments administered electronically will be designed to disallow invalid response values and to flag and alert study personnel to incomplete instruments prior to saving the instrument. The data will be visually checked by the data manager who will record the presence of each assessment battery file for each participant. In the event of the presence of paper data, all hand-computations will be double-checked and all double entered. Web administered screening data and Smartphone data uploaded to the study server will be backed up each evening, and downloaded for local backup and storage with other study data. After checking for accuracy and completeness of each file, all electronic data will be backed up on the project manager's and data manager's computers, and backed up to a secure remote hard drive.

All database files will be password protected, and only study staff will have access to staff computers or the secure remote hard drive. Paper data will be kept in the laboratory in a locked cabinet.

6.2.2 Assessment of Intervention Fidelity

Treatment fidelity will be critically important to preserve since participants will be randomized to 16 different conditions. The coach interface will be programmed to reflect the participant's treatment assignment and will prompt the coach to intervene appropriately, using fidelity checklist items that display prescribed and proscribed intervention elements. The treatment for each condition will also be manualized for training purposes, and all coaches will be trained to deliver all intervention conditions. Telephone sessions will be audiotaped and a 15% sample rated for treatment fidelity on a quarterly basis. If fidelity falls below 80%, coaches will be retrained. Fidelity checklists specify: a) good counseling practices (e.g., positive regard, active listening); b) intended session content (e.g., portion size estimation); c) unintended session content (i.e., contamination such as evidence of texting a participant not assigned to text messaging or recommending meal replacement to a participant not assigned to that condition). [name] will train the coaches on the intervention and [name] will serve as primary fidelity evaluator. Training will initially involve role-play as coach and participant. Next coaches will observe the Co-I's and Coordinator performing sessions with volunteers. Finally each coach will perform a live dress rehearsal of telephone delivery of each treatment session and condition. They will continue to rehearse until fidelity ratings show that each coach can be certified as competent to deliver all sessions for all conditions. DVD recordings of the trainings will be made and retained in case there is a need to train new coaches or retrain existing ones. Coaches will meet with [name] weekly as a group for clinical supervision.

7. Study Timetable

7.1 Study Timeline

The study time line and randomization goals appear in Table 6. As shown, quarters 1, 2, and 3 will be dedicated to completing development of the protocol and study tools. Development activities include completing programming of the Opt-IN app for usability across all Smartphone platforms, programming online lessons, developing and programming algorithms needed to generate session guides, assessments and reports, preparing treatment manuals and fidelity check protocols, and training coaching staff. Recruitment, screening, and randomization activities will commence in Year 1, quarter 4 and continue through Quarter 1 of Year 5. The remainder of Year 5 is for final follow-up, data analyses and report writing.

	Quarter 1 Sept - Nov	Quarter 2 Dec-Feb	Quarter 3 Mar-May	Quarter 4 June-Aug	Total
Year 1	Development				
Year 2	Testing / 15	47	45	45	(152)
Year 3	45	45	45	45	(182)
Year 4	45	45	45	45	(182)
Year 5	44	Data analysis, report writing			(44)
					N=560

7.1.1 Training and Certification

Study-specific training will take place regarding clinical and survey measures, and intervention protocol.

NU requires that all investigators and members responsible for the design and/or conduct of research provide evidence of adequate training in order to maintain IRB approval of a study. The names of the individuals who will be involved in conduct of the research have been provided. They have all completed the course required by Northwestern University for those who will participate in human subjects research, namely, the CITI web-based course in human subject protection and the NU HIPPA training course (www.research.northwestern.edu/research/oprs/irb/education/HIPAA_Presentation_2006.ppt).

At the beginning of our study, «Patient_Name» weighed «Patient_Initial_Weight» pounds. As of the 3-month assessment, «Patient_Name» now weighs «Patient_3month_Weight» pounds. Please refer to the graph below for a more specific outline of weight loss progress over this time frame.

Based on your patient's progress, we propose several behavioral recommendations to support his/her weight loss efforts.

- Encourage your patient to self-weigh regularly.
- Encourage your patient to regularly track caloric intake using the provided Opt-IN Study application.

- Encourage your patient to engage in regular, short bouts of moderate intensity physical activity such as brisk walking.

We greatly appreciate your time. We will send you another progress report in regard to «Patient_Name»'s weight loss progress at the 6-month assessment. Please feel free to contact [name], the Opt-IN study program coordinator ([contact]; [contact]) with any questions.

Sincerely,

[name]., ABPP
Professor of Preventive Medicine, Psychology, and Psychiatry
Director, Center for Behavior and Health
Co-Program Leader for Cancer Prevention
Principle Investigator of the Opt-IN Research Study

Opt-IN PCP Letter – 3-month little weight lost

Date

«Physician_Name»

«Address»

[figure not shown]
«City», «State» «Zip»

**RE: Primary Care Provider Progress Report for Opt-IN Research Study
(IRB#STU00066546) at Northwestern University**

Dear «Physician_Name»,

Your patient, «Patient_Name» DOB: «Patient_DOB», is participating in the Opt-IN research study being conducted in the Department of Preventive Medicine at Northwestern University. Opt-IN is a 6-month behavioral telephone-based weight loss program that encourages participants to follow a low-calorie, low-fat diet and to engage in a moderate level of physical activity, such as brisk walking. As part of the study, we are sending you quarterly reports on your patients' progress.

At the beginning of our study, «Patient_Name» weighed «Patient_Initial_Weight» pounds. As of the 3-month assessment, «Patient_Name» now weighs «Patient_3month_Weight» pounds. Please refer to the graph below for a more specific outline of weight loss progress over this time frame.

Based on your patient's progress, we propose several behavioral recommendations to support his/her weight loss efforts.

- Encourage your patient to continue self-weighing regularly.
- Encourage your patient to continue monitoring caloric intake using the provided Opt-IN Study application.

- Encourage your patient to continue engaging in moderate intensity physical activity such as brisk walking.

We greatly appreciate your time. We will send you another progress report in regard to «Patient_Name»'s weight loss progress at the 6-month assessment. Please feel free to contact [name], the Opt-IN study program coordinator ([contact]; [contact]) with any questions.

Sincerely,

[name]., ABPP
Professor of Preventive Medicine, Psychology, and Psychiatry
Director, Center for Behavior and Health
Co-Program Leader for Cancer Prevention
Principle Investigator of the Opt-IN Research Study

Opt-IN PCP Letter – 3-month met weight loss goal

Wednesday, March 04, 2020

«Physician_Name»

«Address»

[figure not shown]
«City», «State» «Zip»

**RE: Primary Care Provider Progress Report for Opt-IN Research Study
(IRB#STU00066546) at Northwestern University**

Dear «Physician_Name»,

Your patient, «Patient_Name» DOB: «Patient_DOB», is participating in the Opt-IN research study being conducted in the Department of Preventive Medicine at Northwestern University. Opt-IN is a 6-month behavioral telephone-based weight loss program that encourages participants to follow a low-calorie, low-fat diet and to engage in a moderate level of physical activity, such as brisk walking. As part of the study, we are sending you quarterly reports on your patients' progress.

At the beginning of our study, «Patient_Name» weighed «Patient_Initial_Weight» pounds. As of the 3-month assessment, «Patient_Name» now weighs «Patient_3month_Weight» pounds. Please refer to the graph below for a more specific outline of weight loss progress over this time frame.

Based on your patient's progress, we propose several behavioral recommendations to support his/her weight loss efforts.

- Encourage your patient to continue self-weighing regularly.
- Encourage your patient to continue monitoring caloric intake using the provided Opt-IN Study application.

- Encourage your patient to continue engaging in moderate intensity physical activity such as brisk walking.

We greatly appreciate your time. We will send you another progress report in regard to «Patient_Name»'s weight loss progress at the 6-month assessment. Please feel free to contact [name], the Opt-IN study program coordinator ([contact]; [contact]) with any questions.

Sincerely,

[name]., ABPP
Professor of Preventive Medicine, Psychology, and Psychiatry
Director, Center for Behavior and Health
Co-Program Leader for Cancer Prevention
Principle Investigator of the Opt-IN Research Study

Opt-IN PCP Letter – 6-month no weight lost

Date

«Physician_Name»

«Address»

[figure not shown]
«City», «State» «Zip»

**RE: Primary Care Provider Progress Report for Opt-IN Research Study
(IRB#STU00066546) at Northwestern University**

Dear «Physician_Name»,

Your patient, «Patient_Name» DOB: «Patient_DOB», is participating in the Opt-IN research study being conducted in the Department of Preventive Medicine at Northwestern University. Opt-IN is a 6-month behavioral telephone-based weight loss program that encourages participants to follow a low-calorie, low-fat diet and to engage in a moderate level of physical activity, such as brisk walking. As part of the study, we are sending you quarterly reports on your patients' progress.

At the beginning of our study, «Patient_Name» weighed «Patient_Initial_Weight» pounds. As of the 6-month assessment, «Patient_Name» now weighs «Patient_6month_Weight» pounds. Please refer to the graph below for a more specific outline of weight loss progress over this time frame.

Based on your patient's progress, we propose several behavioral recommendations to support his/her continued weight loss efforts.

- Encourage your patient to self-weigh regularly.
- Encourage your patient to track caloric intake using a paper diary, website, or smartphone application.

- Promote engaging in regular, short bouts of moderate intensity physical activity such as brisk walking, to encourage weight loss in the future.

Your patient has completed the Opt-IN research study and we greatly appreciate your time. Please feel free to contact [name], the Opt-IN study program coordinator ([contact]; [contact]) with any questions.

Sincerely,

[name]., ABPP
Professor of Preventive Medicine, Psychology, and Psychiatry
Director, Center for Behavior and Health
Co-Program Leader for Cancer Prevention
Principle Investigator of the Opt-IN Research Study

Opt-IN PCP Letter – 6-month little weight lost

Date

«Physician_Name»

«Address»

[figure not shown]
«City», «State» «Zip»

**RE: Primary Care Provider Progress Report for Opt-IN Research Study
(IRB#STU00066546) at Northwestern University**

Dear «Physician_Name»,

Your patient, «Patient_Name» DOB: «Patient_DOB», is participating in the Opt-IN research study being conducted in the Department of Preventive Medicine at Northwestern University. Opt-IN is a 6-month behavioral telephone-based weight loss program that encourages participants to follow a low-calorie, low-fat diet and to engage in a moderate level of physical activity, such as brisk walking. As part of the study, we are sending you quarterly reports on your patients' progress.

At the beginning of our study, «Patient_Name» weighed «Patient_Initial_Weight» pounds. As of the 6-month assessment, «Patient_Name» now weighs «Patient_6month_Weight» pounds. Please refer to the graph below for a more specific outline of weight loss progress over this time frame.

Based on your patient's progress, we propose several behavioral recommendations to support his/her continued weight loss efforts.

- Encourage your patient to continue self-weighing regularly.
- Encourage your patient to continue monitoring caloric intake using a paper diary, website, or smartphone application.

- Encourage your patient to continue engaging in moderate intensity physical activity such as brisk walking.

Your patient has completed the Opt-IN research study and we greatly appreciate your time. Please feel free to contact [name], the Opt-IN study program coordinator ([contact]; [contact]) with any questions.

Sincerely,

[name]., ABPP
Professor of Preventive Medicine, Psychology, and Psychiatry
Director, Center for Behavior and Health
Co-Program Leader for Cancer Prevention
Principle Investigator of the Opt-IN Research Study

Opt-IN PCP Letter – 6-month met weight loss goal

Date

«Physician_Name»

«Address»

[figure not shown]
«City», «State» «Zip»

**RE: Primary Care Provider Progress Report for Opt-IN Research Study
(IRB#STU00066546) at Northwestern University**

Dear «Physician_Name»,

Your patient, «Patient_Name» DOB: «Patient_DOB», is participating in the Opt-IN research study being conducted in the Department of Preventive Medicine at Northwestern University. Opt-IN is a 6-month behavioral telephone-based weight loss program that encourages participants to follow a low-calorie, low-fat diet and to engage in a moderate level of physical activity, such as brisk walking. As part of the study, we are sending you quarterly reports on your patients' progress.

At the beginning of our study, «Patient_Name» weighed «Patient_Initial_Weight» pounds. As of the 6-month assessment, «Patient_Name» now weighs «Patient_6month_Weight» pounds. Please refer to the graph below for a more specific outline of weight loss progress over this time frame.

Based on your patient's progress, we propose several behavioral recommendations to support his/her continued weight loss or maintenance efforts.

- Encourage your patient to continue self-weighing regularly.

- Encourage your patient to monitor caloric intake using a paper diary, website, or smartphone application if/when weight regains occurs.
- Encourage your patient to continue engaging in moderate intensity physical activity such as brisk walking to prevent weight regain.

Your patient has completed the Opt-IN research study and we greatly appreciate your time. Please feel free to contact [name], the Opt-IN study program coordinator ([contact]; [contact]) with any questions.

Sincerely,

[name]., ABPP
Professor of Preventive Medicine, Psychology, and Psychiatry
Director, Center for Behavior and Health
Co-Program Leader for Cancer Prevention
Principle Investigator of the Opt-IN Research Study

Opt-IN PCP Letter – Incomplete Assessment, 3-month

Wednesday, March 04, 2020

«Physician_Name»
«Physician_Address»
«Physician_City_State_Zip»

**RE: Primary Care Provider Progress Report for Opt-IN Research Study
(IRB#STU00066546) at Northwestern University**

Dear «Physician_Name»,

Your patient, «Patient_Name» DOB: «Participant_DOB», is participating in the Opt-IN research study being conducted in the Department of Preventive Medicine at Northwestern University. Opt-IN is a 6-month behavioral telephone-based weight loss program that encourages participants to follow a low-calorie, low-fat diet and to engage in a moderate level of physical activity, such as brisk walking. As part of the study, we are sending you quarterly reports on your patients' progress.

Unfortunately, your patient has not completed the 3 month follow-up assessment, so we are unable to provide you with a weight loss progress report. There are documented benefits from weight loss, physical activity and a healthy diet. The aim of our study is to find an effective way to increase these behaviors and outcomes. The participation of your patient in this study will help us achieve our goal. We hope that you will encourage the patient to do so.

We greatly appreciate your time. We will send you another progress report in regard to «Patient_Name»'s weight loss progress at the 6-month assessment. Please feel free to contact [name], the Opt-IN study program coordinator ([contact]; [contact]) with any questions.

Sincerely,

[name]., ABPP
Professor of Preventive Medicine, Psychology, and Psychiatry
Director, Center for Behavior and Health
Co-Program Leader for Cancer Prevention
Principle Investigator of the Opt-IN Research Study

Opt-IN PCP Letter – Incomplete Assessment, 6-month

Wednesday, March 04, 2020

«Physician_Name»
«Physician_Address»
«Physician_City_State_Zip»

**RE: Primary Care Provider Progress Report for Opt-IN Research Study
(IRB#STU00066546) at Northwestern University**

Dear «Physician_Name»,

Your patient, «Patient_Name» DOB: «Participant_DOB», is participating in the Opt-IN research study being conducted in the Department of Preventive Medicine at Northwestern University. Opt-IN is a 6-month behavioral telephone-based weight loss program that encourages participants to follow a low-calorie, low-fat diet and to engage in a moderate level of physical activity, such as brisk walking. As part of the study, we are sending you quarterly reports on your patients' progress.

Unfortunately, your patient has not completed the 6 month follow-up assessment, so we are unable to provide you with a weight loss progress report. There are documented benefits from weight loss, physical activity and a healthy diet. The aim of our study is to find an effective way to increase these behaviors and outcomes. The participation of your patient in this study will help us achieve our goal. We hope that you will encourage the patient to do so.

Your patient has completed the Opt-IN research study and we greatly appreciate your time. Please feel free to contact [name], the Opt-IN study program coordinator ([contact]; [contact]) with any questions.

Sincerely,

[name]., ABPP
Professor of Preventive Medicine, Psychology, and Psychiatry
Director, Center for Behavior and Health
Co-Program Leader for Cancer Prevention
Principle Investigator of the Opt-IN Research Study

Opt-IN Study
Department of Preventive Medicine
Suite 1400
[name]
Chicago, IL 60611
[contact]
[contact]

PARTICIPANT NAME/ADDRESS

DATE

Dear **NAME**,

I hope this letter finds you well! We want to thank you for being a participant in the Opt-IN study and your contribution to our research knowledge about health and weight loss!

